# **INTRODUCTION:**

Battlefield acupuncture is an auricular therapy (Ear acupuncture) which has been in existence for centuries, with roots tied to Eastern Asian medicine. Ease of application, low cost, and minimal side effects make battlefield acupuncture a perioperative modality that has been linked to decreased morbidity and mortality in patients undergoing surgical procedures and anesthesia (1). In the United States, there is pressure by government and the medical community to decrease opioid use, especially in the perioperative time period. Opiate use due to postoperative pain, postoperative nausea and vomiting (PONV), perioperative anxiety have all been linked to increased hospital stays, increased morbidity and mortality, and ultimately higher healthcare costs (2). Anesthesia providers can be trained in application of acupuncture in the perioperative time period. Through analysis of rates of postoperative opioid use, postoperative nausea and vomiting and perioperative anxiety, the efficacy and utility of battlefield acupuncture will be realized as an effective adjunct to multimodal anesthesia care.

# **HYPOTHESIS AND OUTCOMES:**

The study hypothesis is that perioperative battlefield acupuncture for general surgery and urology cases undergoing general anesthesia will decrease opioid requirements, postoperative pain, the incidence of PONV, and the incidence of perioperative anxiety in comparison to simulated (placebo) perioperative battlefield acupuncture.

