#### **Anesthetic Plan:**

The anesthetic management will be general anesthesia with the provision of intravenous opioids intraoperatively and during recovery. Fentanyl will be the sole intra operative opioid. No other alterations of anesthetic management will take place pre or intra operatively. The battlefield acupuncture or sham battlefield acupuncture will be placed in the postoperative care unit (PACU).

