### **Techniques:**

The treatment group (Group 1) will receive postoperative auricular battlefield acupuncture. The control group (Group 2) will receive sham (placebo) postoperative auricular battlefield acupuncture as described above.

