### Data:

Data gathering will be performed by [name], MD and/or a CRNA. Data collection will occur in the PACU (Post-Anesthesia Care Unit) before the PACU nurses evaluate the patient for discharge. Assessment will occur at 1 hour and 24 hour post procedure. The assessment will occur on the next day by either a medical student and/or CRNA at the patients' bed side.

Assessment of the battlefield acupuncture efficacy will be performed by testing the incidence of PONV, incidence of postoperative anxiety, and pain. Pain will be assessed via the visual analog scale (VAS) scoring system.

A study investigator will record the following:

- 1. At times 1 hour and 24 hours the following will be assessed:
- 2. Incidence of PONV
- 3. Incidence of postoperative anxiety
- 4. Pain score on an 11-point (0 to 10) Visual Analog Scale (VAS) at rest and with activity
- 5. Postoperative opioid consumption via morphine equivalents used
- 6. Patient satisfaction with analgesia score (0 to 100%)

7. Any occurrence of acupuncture site infection, acupuncture site bleeding, allergic reaction to acupuncture needles, or scar tissue formation at site of acupuncture needle.

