#### **Benefits:**

A direct benefit to patients may be a decrease in post-operative opioid requirements, decreased postoperative pain decreased incidence of PONV and decreased perioperative anxiety.

The societal benefits to participating in this study may be improved knowledge of anesthesia practice methods in improving post-operative pain control and reducing side effects for patients in the future. There is no financial benefit to participating in this study.

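### The hypothesis names perioperative acupuncture and perioperative anxiety, but the trial treats only in the PACU and records only postoperative anxiety, with no baseline

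*Combined protocol and SAP*

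**What the plan says.** All references are to the combined protocol and SAP.

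The aims use the wide window. Hypothesis and Outcomes states that perioperative acupuncture "will decrease opioid requirements, postoperative pain, the incidence of PONV, and the incidence of perioperative anxiety in comparison to simulated (placebo) perioperative battlefield acupuncture". The Introduction proposes to judge efficacy "Through analysis of rates of postoperative opioid use, postoperative nausea and vomiting and perioperative anxiety". Benefits lists, among the possible direct gains to patients, "decreased postoperative pain decreased incidence of PONV and decreased perioperative anxiety".

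The methods use a narrower one. The Anesthetic Plan states: "The battlefield acupuncture or sham battlefield acupuncture will be placed in the postoperative care unit (PACU)". Techniques states: "The treatment group (Group 1) will receive postoperative auricular battlefield acupuncture". The Data section lists "incidence of postoperative anxiety" among the items recorded at 1 hour and 24 hours. The Statistical Analysis section works with those two time points and plans Fisher's exact test for 2x2 tables. No anxiety assessment before surgery is described, and the Data section gives no anxiety instrument or threshold.

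On opioids, the hypothesis leaves the period open. The Introduction, Data and Benefits sections all limit it to the postoperative period.

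**The concern.** Anxiety before surgery, and intraoperative fentanyl, both precede the moment at which the arms begin to differ. The study treatment cannot change either, and the outcome list covers neither. A reader who takes the hypothesis at its word would expect a period that the trial does not test. A positive result could then be credited to more than PACU-placed treatment, and a null result could be taken as evidence against a perioperative benefit of which only the postoperative part was examined.

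The missing baseline adds to this. The exclusion criteria remove psychiatric disorders only where they may interfere with pain assessment, so patients who are already anxious can enrol. If still anxious afterwards, they count towards the postoperative incidence although they are not new cases. In a trial of 72, an unlucky split of such patients between the arms could be neither seen nor allowed for.

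**Working it through.** **Step 1. Set the sections side by side.**

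| Element | Aims (Introduction, Hypothesis, Benefits) | Methods (Anesthetic Plan, Techniques, Data, Statistical Analysis) |
|---|---|---|
| Treatment period | Perioperative (Hypothesis) | Postoperative, in the PACU, both arms |
| Anxiety | Perioperative (all three sections) | Postoperative, at 1 and 24 hours |
| Opioids | Unqualified in Hypothesis; postoperative in Introduction and Benefits | Postoperative consumption |
| Preoperative anxiety | Not mentioned separately | Not recorded |

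The anxiety wording therefore differs in three sections. The opioid wording and the description of the trial's own treatment differ in the hypothesis only.

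**Step 2. The plan's own figure.** The only sample-size statement is 72 (36 per group), for a 33% reduction in opioid consumption treated as binary, at 80% power. No power is stated for anxiety. The control rate is not given, and neither is whether the 33% is absolute or relative, so the figure cannot be uniquely reproduced. The two-sided pooled formula is

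n per arm = [1.96 √(2p̄(1−p̄)) + 0.842 √(p1(1−p1) + p2(1−p2))]² / (p1−p2)².

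- Absolute 33 points, assumed control rates of about 0.60 to 0.70: 35 per arm.
- Relative 33%: 33 per arm at an assumed control rate of 0.90, and 40 at 0.85.

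So 36 is attainable under some assumptions. None of this depends on anxiety, and rewording the anxiety aim changes no sample-size figure.

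**Step 3. Does carried-in anxiety bias the comparison?** Let b be the proportion anxious before surgery, r the proportion of those still anxious afterwards, and s the proportion newly anxious among the rest. The postoperative rate in an arm is b·r + (1−b)·s. Randomisation gives both arms the same expected b, so carried-in cases produce no bias. The observed rate does mix b·r (persisting) with (1−b)·s (new), and without b the two cannot be separated.

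**Step 4. How large can chance imbalance in b be?** With 36 per group, SE = √(2·b·(1−b)/36). The documents give no b, so a range is assumed.

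- b = 0.20: √(0.32/36) = 0.094
- b = 0.30: √(0.42/36) = 0.108
- b = 0.50: √(0.50/36) = 0.118

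This is about 9 to 12 percentage points.

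**Step 5. What reaches the outcome?** An imbalance of Δb moves the postoperative difference by Δb·(r−s), which is less than Δb itself. With assumed r = 0.70 and, as a limiting case, s = 0, one standard error of imbalance moves the difference by 0.70 × 9.4 = 6.6 to 0.70 × 11.8 = 8.3 points. The Fisher test's error rate already allows for this variation. What is lost without a baseline is the ability to see it and remove it.

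**The case against.** The strongest reply is that *perioperative* ordinarily includes the postoperative phase. On that reading, acupuncture in the PACU with anxiety assessed afterwards lies inside the stated aim, the operative sections agree with one another, and only wording is at issue. Much of this stands. A reader might infer that the trial cannot answer its anxiety question at all. The documents do not support that: the arms are randomised against sham and can be compared on postoperative anxiety. What does not stand is that the wording is harmless. The hypothesis itself sets postoperative pain beside perioperative anxiety, so the two words appear to mark different periods, and the Data section then changes the word for anxiety.

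A reader might also infer that patients already anxious before surgery bias the result. They do not: in expectation they are equally frequent in both arms, and persisting anxiety is a legitimate target of treatment.

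Nor is the opioid wording at fault throughout. The Introduction and Benefits already say postoperative. The Introduction's description of the technique as a perioperative modality is cited background and should not be altered.

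Finally, it is fair to say that a baseline question presupposes a defined anxiety measure, which the Data section lacks, and that new and persisting cases will be small groups at 36 per arm. Both points limit the remedy to a simple form but do not remove the case for it.

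**Conclusion.** The point holds as a mismatch between the stated aim and the design. The trial can compare PACU-placed acupuncture with sham on postoperative anxiety at 1 and 24 hours. It cannot support a statement about anxiety before or during surgery, and it cannot tell new from persisting anxiety.

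The mismatch is read directly from the text and needs no assumed figure. The size of possible chance imbalance, a standard error of about 9 to 12 percentage points, rests on an assumed baseline prevalence of 20% to 50% and on 36 per group. It concerns precision and interpretation, not bias. The matter is a cheap and worthwhile improvement, not a defect that invalidates the anxiety comparison. How results will eventually be reported cannot be known from the plan; the amendment simply removes the opening for a wider claim.

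**What to change.** 1. **Hypothesis and Outcomes.** Reconcile the wording with the methods: describe the intervention as postoperative (PACU-placed), anxiety as postoperative anxiety, and opioid requirements as postoperative opioid requirements.
2. **Introduction and Benefits.** Change only the anxiety wording, to postoperative. Leave the opioid wording and the cited background as they are.
3. **Data.** Record anxiety once at the preoperative consent contact, before the allocation is known, with the same question and threshold as at 1 and 24 hours. The question and threshold must first be written into this section.
4. **Statistical Analysis.** Keep the Fisher test. Add a baseline-adjusted comparison of postoperative anxiety, for example a Mantel-Haenszel estimate stratified by baseline anxiety, or logistic regression. A Mantel-Haenszel risk difference stays on the scale of the unadjusted difference in proportions. A logistic model gives a conditional odds ratio, which should be labelled as such. Report new and persisting cases by arm descriptively, without tests.

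The cost is one extra question at a contact that already takes place, a small added analysis, a protocol amendment and a narrower claim. Treatment timing and sample size are untouched. A baseline cannot be recovered after surgery, so item 3 has to be in place before patients are enrolled.

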# **STUDY DESIGN AND METHODS**

2

This will be a prospective randomized study to compare auricular battlefield acupuncture to sham auricular battlefield acupuncture in patients undergoing general surgery and urology cases with general anesthesia. Participants in the study will be randomly assigned to either receive auricular battlefield acupuncture (treatment group) or simulated (placebo; control group) auricular battlefield acupuncture. Battlefield acupuncture needles will be utilized in the test arm and blunt needle pressing and covering with acupuncture stickers will be utilized in the control arm as a sham treatment. Location of needles and stickers will be placed according to 5 VA approved BFA auricular acupuncture points associated with PONV, pain, and anxiety respectively (Figure 1; 3). In both arms, the treatment ear will be covered after treatment so as to blind the patient. Both battlefield acupuncture and control groups will receive small band aids on the battlefield acupuncture needle sites. Both the evaluators for post procedure assessment along with the patient will be blinded in regards to what group they are in.

Figure 1. Battlefield acupuncture points.

Source: Teresa M. Kerge et al 2013.US Service Members With Polytrauma. Practical Pain Managementhttp://www.practicalpainmanagement.c om/pain/spine/trauma/us-servicemembers-polytrauma

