#### **Exclusion Criteria:**

- 1 Coagulopathies
- 2 Patients with continuous epidural
- 3 Uncooperative patient
- 4 Psychiatric disorders and language deficiencies that may interfere with the assessment of pain
- 5 Insufficient understanding of the pain scoring system.
- 6 Outpatient stay

This study will be performed at the John D. Dingell VA Medical Center. Only a trained MD anesthesiologist will recruit patient in the preoperative period, where informed consent will be obtained. Computerized randomization will take place at the time the patient presents for surgery. Consent will be taken preoperatively.

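### Blinding covers only the patient and the evaluators, so PACU staff who see placement, or anyone with access to the allocation, can know the arm while opioids are given

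*Combined protocol and SAP*

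**What the plan says.** The section STUDY DESIGN AND METHODS names who is blinded: "Both the evaluators for post procedure assessment along with the patient will be blinded in regards to what group they are in". No other group is named anywhere in the document.

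The two procedures differ to an onlooker: "Battlefield acupuncture needles will be utilized in the test arm and blunt needle pressing and covering with acupuncture stickers will be utilized in the control" group. Concealment comes afterwards. "Both battlefield acupuncture and control groups will receive small band aids on the battlefield acupuncture needle sites", and "In both arms, the treatment ear will be covered after treatment so as to blind the patient". The Acupuncture Plan repeats that the bandage is there to blind the patient.

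The Anesthetic Plan fixes the place: "The battlefield acupuncture or sham battlefield acupuncture will be placed in the postoperative care unit (PACU"). The same section describes "general anesthesia with the provision of intravenous opioids intraoperatively and during recovery". It does not say who decides recovery doses or on what basis.

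On timing, the text after the Exclusion Criteria states: "Computerized randomization will take place at the time the patient presents for surgery". The allocation therefore exists before the patient reaches the PACU, and the document does not say who holds it.

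Among the items recorded at 1 and 24 hours, the Data section lists "Postoperative opioid consumption via morphine equivalents used". Opioid requirement is the first item in the study hypothesis and the only outcome used for the sample size in Statistical Analysis.

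**The concern.** Blinding the evaluator protects outcomes that an evaluator rates. Opioid consumption is different. By the time it is recorded the doses have been given, and the evaluator only totals them. If someone who influences those doses knows the arm, expectation can affect the total: a little less for patients known to have needles, a little more for those known to have sham. The difference would look like an opioid-sparing effect whether or not acupuncture works.

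The plan brings the ingredients together. The arm is visible during placement, placement happens where recovery opioids are provided, and the people there are outside the stated blind. A positive opioid result could then not be separated from staff expectation, and this is the outcome the trial is sized on.

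**Working it through.** **Who could learn the arm, from the text**

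| Group | Stated as blinded? | Could see placement? | What they see later |
|---|---|---|---|
| Patient | Yes | Sham is meant to imitate the procedure | Covered ear |
| Post-procedure evaluators | Yes | Must not, if they are to be blinded | Covered ear |
| PACU staff present at placement | No | Yes; no screening is described | Covered ear, arm already seen |
| Staff who first see the patient later, such as on the ward | No | No | Covered ear in both arms |
| Anyone with access to the allocation | No | Not needed | Arm known from the record |

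The gap lies mainly in the third and fifth rows. The fourth is partly protected by the band aids and bandage.

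**The plan's own figure**

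Statistical Analysis gives 72 participants (36 per group) for 80% power at p<0.05, from a 33% reduction treated as a binary outcome. The control rate is missing, as is whether 33% is absolute or relative, so 72 cannot be reproduced from the stated inputs alone. The usual two-sided pooled formula without continuity correction is

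n per group = [1.96·√(2p̄(1−p̄)) + 0.842·√(p₁(1−p₁)+p₂(1−p₂))]² / (p₁−p₂)².

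- Absolute 33-point drop, for example 0.665 versus 0.335: (1.386 + 0.562)² / 0.33² = 34.8, so 35 per group. Control rates of 0.59 to 0.74 all give 35. Power with 36 per group in the example is 81.3%.
- Relative 33% drop: a match (36 to 37 per group) only at control rates of about 0.87 to 0.88.

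The blinding point does not depend on this figure. Only the 36 per group is used below.

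**Illustration of what a staff-induced shift would do**

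Assumptions, none of them in the documents: no true acupuncture effect; opioid use analysed as a continuous variable, as the planned t-test would do; normal approximation; staff knowledge shifts mean use in one arm by b standard deviations.

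- Standard error of the difference = √(2/36) = 0.236 SD.
- Displacement of the test statistic: d = b / 0.236.
- Chance of a significant result = P(Z > 1.96 − d) + P(Z < −1.96 − d).

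| Shift b (SD) | d | Chance of p<0.05 |
|---|---|---|
| 0 | 0 | 5.0% |
| 0.1 | 0.42 | 7.1% |
| 0.2 | 0.85 | 13.6% |
| 0.3 | 1.27 | 24.7% |

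To read these shifts as percentages an SD is needed, and the documents give none. If the coefficient of variation were between 0.6 and 1.0, then 0.1 SD would be 6-10% of mean use (0.1 × 0.6 to 0.1 × 1.0) and 0.3 SD would be 18-30%.

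**The case against.** The best defence is that the plan conceals more than its blinding sentence suggests. Both arms get band aids and a bandaged ear. These are there for the patient's sake, but they also hide the arm from anyone who did not watch placement. Much of the 24-hour observation period may fall to such staff. This stands, and it confines the main exposure to those at placement and those with access to the allocation.

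Several stronger readings are tempting, and the documents do not support them.

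- A reader might infer that the person who places the needles may also collect outcomes, because the Data section allows a physician or CRNA to gather data without separating the roles. The requirement that evaluators be blinded already rules this out, since whoever places needles or sham knows the arm. What remains is a request for clarification.
- A reader might infer that PACU staff decide every dose and will know the arm. The Anesthetic Plan says only that intravenous opioids are provided during recovery. It does not say who decides, or how far dosing is driven by the patient. The document fails to prevent knowledge of the arm; it does not state that staff will have it.
- A reader might express a bias as a share of the 33% reduction behind the sample size. That figure is described as a binary-outcome rate, so it may not be on the same scale as a percentage change in mean consumption.
- A reader might take the false-positive rates as estimates. The shift is assumed, and a leak centred on the PACU need not carry through to the 24-hour total.

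None of this closes the gap. No section blinds the staff who order or give postoperative opioids, screens placement from them, or says who holds the allocation.

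**Conclusion.** The concern holds in this form. Followed as written, the plan leaves opioid consumption open to performance bias, mainly through PACU staff present at placement and anyone with access to the allocation. Blinded evaluators cannot remove it, because it enters before they measure anything. This rests on one premise beyond the text: that opioid consumption depends at least partly on staff decisions. If dosing were wholly patient-controlled the bias would be smaller, but the documents do not say that it is.

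Confidence is high for the omission and does not extend to the size of the bias, which cannot be computed from the documents. The rise from 5% to about 7-25%, for assumed shifts of 0.1 to 0.3 SD with 36 per group, shows only that a modest shift would matter in a trial of this size. The gap should be closed, since the change is procedural and cheap.

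**What to change.** In STUDY DESIGN AND METHODS and the Anesthetic Plan:

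- extend the blind to the PACU and ward staff who order or give postoperative opioids;
- place needles or sham screened from the view of those staff, and apply the same ear cover in both arms before they can see the ear;
- keep the allocation out of the bedside chart and known only to the person placing the needles, and state this from the time of randomization onward.

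In the Data section, state as clarification of the existing evaluator blinding that the person placing needles or sham does not collect outcome data. Where existing staffing allows, state also that this person does not direct that patient's postoperative opioids.

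The cost is protocol wording, a few minutes of screened placement per patient, and an unblinded contact who must be reachable for ear-site problems. It is the view of the ear during placement that must be screened, so the change need not take staff away from the patient. The documents do not show whether the placer can always be kept apart from opioid orders without extra staff, which is why that part is conditional. The sample size is unchanged, and no dose, schedule or clinical rule is altered.

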#### **Inclusion Criteria:**

1- Patients with an American Society of Anesthesiologists (ASA) Physical Status classification of 1 to 4

2 - Patients aged between 18 and 100 scheduled to undergo scheduled suitable

inpatient/outpatient cases under anesthesia.

3 - Patients must be willing and fit to give written informed consent

4 - Inpatient stay required

